**7.3.7.1. Progression-Free Survival by RECIST v1.1**

Under RECIST v1.1, PFS is defined as the length of time between the baseline visit (Day 1) and the earlier of death or first assessment of PD as assessed by RECIST v1.1.

**7.3.7.2. Progression-Free Survival by mRECIST v1.1**

Under mRECIST v1.1, PFS is defined as the length of time between the baseline visit (Day 1) and the earlier of death or first confirmed assessment of PD (as described in Section [7.3.2.3 Table 6](#)).

### 7.3.8. Overall Survival

Overall survival is defined as the interval between Cycle 1 Day 1 and the date of death due to any cause. Date of death will be determined using the Death Report, the Survival Follow-Up, and the Subject Status CRFs. Subjects who are lost-to-follow-up or still alive at the time of analysis will be right-censored at the earlier of the date the subject was last known alive and the clinical data cutoff date for the analysis. The last known alive date is defined as the later of the last study visit and the date the subject was last known alive from the Survival Follow-Up and Subject Status CRFs.

Kaplan-Meier time to event curves will be presented by treatment groups. Median survival will be estimated using the KM method. Kaplan-Meier estimates of 1-year and 2-year survival probabilities will be provided. Confidence intervals for median survival time will be calculated using the method of Brookmeyer and Crowley (1982).

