### 5.2. Treatment Groups

This is a Phase 1/2, open-label, nonrandomized, multicenter, dose-escalation study. In Phase 1, because the starting dose of INCAGN01876 is 1.0 mg/kg in Cohort 3, up to 4 doses of INCAGN01876 will be tested. Data will be summarized by treatment group and by dose level.

Dose escalation of the triplet immune therapy combinations will begin enrolling once all of the applicable doublet combinations have cleared 3 INCAGN01876 dose levels (see [Table 1](#)) or the MTD or PAD of INCAGN01876 has been determined (whichever occurs first). The starting dose of INCAGN01876 will be 2 dose levels below the last dose cohort deemed safe in the doublet combination. The triplet immune therapy combinations will be explored in parallel as outlined in [Figure 1](#).

- Treatment Group A:
  - INCAGN01876 1.0 mg/kg + nivolumab 240 mg
  - INCAGN01876 3.0 mg/kg + nivolumab 240 mg
  - INCAGN01876 5.0 mg/kg + nivolumab 240 mg
  - INCAGN01876 10.0 mg/kg + nivolumab 240 mg
- Treatment Group B
  - 1.0 mg/kg run-in with INCAGN01876 × 2 doses followed by nivolumab 240 mg
  - 3.0 mg/kg run-in with INCAGN01876 × 2 doses followed by nivolumab 240 mg
  - 5.0 mg/kg run-in with INCAGN01876 × 2 doses followed by nivolumab 240 mg
  - 10.0 mg/kg run-in with INCAGN01876 × 2 doses followed by nivolumab 240 mg
- Treatment Group C
  - INCAGN01876 1.0 mg/kg + ipilimumab 1 mg/kg
  - INCAGN01876 3.0 mg/kg + ipilimumab 1 mg/kg
  - INCAGN01876 5.0 mg/kg + ipilimumab 1 mg/kg
  - INCAGN01876 10.0 mg/kg + ipilimumab 1 mg/kg

- Treatment Group D
  - INCAGN01876 1.0 mg/kg + nivolumab 3 mg/kg + ipilimumab 1 mg/kg
  - INCAGN01876 3.0 mg/kg + nivolumab 3 mg/kg + ipilimumab 1 mg/kg
  - INCAGN01876 5.0 mg/kg + nivolumab 3 mg/kg + ipilimumab 1 mg/kg
  - INCAGN01876 10.0 mg/kg + nivolumab 3 mg/kg + ipilimumab 1 mg/kg
- Treatment Group E
  - 1.0 mg/kg run-in with INCAGN01876 × 2 doses followed by nivolumab 3 mg/kg + ipilimumab 1 mg/kg
  - 3.0 mg/kg run-in with INCAGN01876 × 2 doses followed by nivolumab 3 mg/kg + ipilimumab 1 mg/kg
  - 5.0 mg/kg run-in with INCAGN01876 × 2 doses followed by nivolumab 3 mg/kg + ipilimumab 1 mg/kg
  - 10.0 mg/kg run-in with INCAGN01876 × 2 doses followed by nivolumab 3 mg/kg + ipilimumab 1 mg/kg

In Phase 2, endometrial, gastric, SCCHN subjects and a separate biopsy cohort will be enrolled in each treatment group. Data will be summarized by treatment group and tumor type-specific cohort.

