- Treatment Group J with SCCHN cancer

- Treatment Group K with adenocarcinoma of the endometrium
- Treatment Group K with gastric cancer
- Treatment Group K with SCCHN cancer
- Treatment Group L with adenocarcinoma of the endometrium
- Treatment Group L with gastric cancer
- Treatment Group L with SCCHN cancer

Table summaries, unless otherwise indicated, will be provided by treatment group and tumor type-specific cohort.

- **Phase 2 FAS INCAGN01876 Population**

The Phase 2 FAS population includes all subjects in the FAS population who are enrolled in the Phase 2 portion of the study and received at least 1 dose of INCAGN01876.

- **Phase 2 FAS Weighted Nivolumab Population**

The Phase 2 FAS weighted nivolumab population includes all subjects in the FAS population who are enrolled in the Phase 2 portion of the study and received at least 1 dose of nivolumab administered in mg/kg. This includes subjects enrolled into Treatment Groups J, K, and L.

- **Phase 2 FAS Fixed Nivolumab Population**

The Phase 2 fixed FAS nivolumab population includes all subjects in the FAS population who are enrolled in the Phase 2 portion of the study and received at least 1 dose of nivolumab administered in mg. This includes subjects enrolled into Treatment Groups F, G, and H.

- **Phase 2 FAS Ipilimumab Population**

The Phase 2 FAS ipilimumab population includes all subjects enrolled in the Phase 2 portion of the study who received at least 1 dose of ipilimumab.

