#### **7.3.7. Progression-Free Survival**

Progression-free survival is defined as the length of time between the baseline visit (Day 1) and the earlier of death or PD as assessed by RECIST v1.1 and mRECIST v1.1. Date of death will be determined using the Death Report CRF.

Censoring for PFS will follow the algorithm outlined in [Table 7](#) which is based on the FDA – Guidance for Industry: Clinical Trial Endpoints for the Approval of Cancer Drugs and Biologics (FDA 2007).

Kaplan-Meier curves for PFS will be presented by cohort-specific tumor types. The KM estimate of median PFS will be presented with its 95% CI. The 95% CI will be calculated using the Brookmeyer and Crowley's method ([Brookmeyer and Crowley 1982](#)).

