2.1.1.2	Summary of Unconfirmed Best Response Under RECIST v1.1 - by Treatment Group and Tumor Type	Phase 2 Response Population		X
2.2.1	Summary of Unconfirmed Best Response, Duration of Response, and Duration of Disease Control Under RECIST v1.1 - by Treatment Group and Dose	Phase 1 Response Evaluable Population		X
2.2.2	Summary of Unconfirmed Best Response, Duration of Response, and Duration of Disease Control Under mRECIST v1.1 - by Treatment Group and Dose	Phase 1 Response Evaluable Population		X
2.2.3.1	Summary of Confirmed Best Response, Duration of Response, and Duration of Disease Control Under mRECIST v1.1 - by Treatment Group and Tumor Type	Phase 2 Response Evaluable Population		X
2.2.3.2	Summary of Unconfirmed Best Response Under mRECIST v1.1 - by Treatment Group and Tumor Type	Phase 2 Response Evaluable Population		X
2.4.1	Summary of Progression-Free Survival Under RECIST v1.1	Phase 1 FAS Population		X
2.4.2	Summary of Progression-Free Survival Under RECIST v1.1 - by Tumor Type	Phase 2 FAS Population		X
2.5.1	Summary of Progression-Free Survival Under mRECIST v1.1	Phase 1 FAS Population		X
2.5.2	Summary of Progression-Free Survival Under mRECIST v1.1 - by Tumor Type	Phase 2 FAS Population		X
2.6.1	Summary of Overall Survival	Phase 1 FAS Population		X
2.6.2	Summary of Overall Survival - by Tumor Type	Phase 2 FAS Population		X

Table No.	Title	Population	Standard	In-Text
Safety				
3.1 Dose Exposure				
3.1.1.1	Summary of Drug Exposure to INCAGN01876 - by Treatment Group and Dose	Phase 1 FAS INCAGN01876 Population		X
3.1.1.2	Summary of Drug Exposure to INCAGN01876 - by Treatment Group and Tumor Type	Phase 2 FAS INCAGN01876 Population		X
3.1.2.1	Summary of Drug Exposure to Nivolumab - by Treatment Group and Dose	Phase 1 FAS Fixed Nivolumab Population		X
3.1.2.2	Summary of Drug Exposure to Nivolumab - by Treatment Group and Dose	Phase 1 FAS Weighted Nivolumab Population		X
3.1.2.3	Summary of Drug Exposure to Nivolumab - by Treatment Group and Tumor Type	Phase 2 FAS Fixed Nivolumab Population		X
3.1.2.4	Summary of Drug Exposure to Nivolumab - by Treatment Group and Tumor Type	Phase 2 FAS Weighted Nivolumab Population		X
3.1.3.1	Summary of Drug Exposure to Ipilimumab - by Treatment Group and Dose	Phase 1 FAS Ipilimumab Population		X
3.1.3.2	Summary of Drug Exposure to Ipilimumab - by Treatment Group and Tumor Type	Phase 2 FAS Ipilimumab Population		X

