## Figures

Figure No.	Title	Population
4.1 Efficacy		
4.1.1	Kaplan-Meier Estimates of Progression-Free Survival	Phase 2 FAS Population
4.1.2	Kaplan-Meier Estimates of Overall Survival	Phase 2 FAS Population
4.1.3.1	Swim Plot of Duration of Response - by Treatment Group	Phase 1 FAS Population
4.1.3.2	Swim Plot of Duration of Response - by Treatment Group and Tumor Type	Phase 2 FAS Population
4.1.4.1	Waterfall Plot of Percentage Change From Baseline in Sum of Target Lesions - by Treatment Group and Dose	Phase 1 FAS Population
4.1.4.2	Waterfall Plot of Percentage Change From Baseline in Sum of Target Lesions - by Treatment Group and Tumor Type	Phase 2 FAS Population
4.1.5.1	Spider Plot of Percentage Change From Baseline in Sum of Target Lesions - by Treatment Group	Phase 1 FAS Population
4.1.5.2	Spider Plot of Percentage Change From Baseline in Sum of Target Lesions - by Treatment Group and Tumor Type	Phase 2 FAS Population
4.90 Safety Data		
4.90.1.1	Bar Chart for Incidence of Treatment Emergent Adverse Events of Special Interest - by Treatment Group and Dose	Phase 1 FAS Population
4.90.1.2	Bar Chart for Incidence of Treatment Emergent Adverse Events of Special Interest - by Treatment Group and Tumor Type	Phase 2 FAS Population
4.90.2.1	Line Graph of Selected Laboratory Values by Study Visit	Phase 1 FAS Population
4.90.2.2	Line Graph of Selected Laboratory Values by Study Visit	Phase 2 FAS Population
4.90.3.1	Box-and-Whisker Plot of Selected Laboratory Values by Study Visit	Phase 1 FAS Population
4.90.3.1	Box-and-Whisker Plot of Selected Laboratory Values by Study Visit	Phase 2 FAS Population

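### Phase 2 overall survival curves are set by treatment group alone, so each curve pools tumor cohorts whose relative sizes depend on the futility stops

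*SAP*

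**What the plan says.** SAP 7.3.8 (Overall Survival) says of the plots: "Kaplan-Meier time to event curves will be presented by treatment groups". The next sentences cover the summary statistics and name no grouping: "Median survival will be estimated using the KM method", then "Kaplan-Meier estimates of 1-year and 2-year survival probabilities will be provided".

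Elsewhere the SAP works at tumor-cohort level:

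- SAP 7.3.7: "Kaplan-Meier curves for PFS will be presented by cohort-specific tumor types". SAP 7.3.3 uses the same grouping for DOR curves.
- SAP 5.2, on Phase 2: "Data will be summarized by treatment group and tumor type-specific cohort".
- SAP 5.3.1: "Table summaries, unless otherwise indicated, will be provided by treatment group and tumor type-specific cohort".
- SAP Appendix A, Table 2.6.2 (Phase 2 full analysis set, in-text): "Summary of Overall Survival - by Tumor Type".
- SAP Appendix A, Figure 4.1.2 (Phase 2 full analysis set): "Kaplan-Meier Estimates of Overall Survival", with no breakdown in the title.

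**The concern.** Phase 2 is built on the tumor cohort within a treatment group. Each such cohort has its own null and target response rates, its own Simon design and its own conclusion. An OS curve for a whole treatment group is not at that level. It averages different diseases, and in Group F it also averages immunotherapy-naive subjects with subjects whose disease was refractory to or relapsed after PD-1 or PD-L1 therapy.

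The averaging weights are not fixed in advance. A cohort that responds grows and one that does not is stopped, so the tumor mix behind the curve is itself a result of the trial. One- and two-year OS is a named secondary objective, and the OS figure is where many readers will look first. Two groups' curves could differ only because different cohorts passed Stage 1.

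**Working it through.** **1. Groupings side by side**

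| Output | Grouping stated |
|---|---|
| PFS curves (SAP 7.3.7) | tumor cohort |
| DOR curves (SAP 7.3.3) | tumor cohort |
| OS curves (SAP 7.3.8) | treatment group |
| OS median, 1- and 2-year rates (SAP 7.3.8) | none stated |
| Figure 4.1.2, OS | none stated |
| Table 2.6.2, OS, Phase 2 | tumor type |
| Default, Phase 2 data and tables (SAP 5.2, 5.3.1) | treatment group by tumor cohort |

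For the figure, the only specific instruction is the 7.3.8 sentence.

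**2. What is pooled.** SAP 2.1 keeps the SAP in force for later protocol amendments unless it is itself amended. In Protocol Table 5, the visible Group F cohorts are cervical, gastric, SCCHN, relapsed melanoma and PD-1 refractory SCCHN. The SAP's own list has endometrial, gastric, SCCHN and a biopsy cohort in each Phase 2 group.

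**3. Cohort size depends on response.** For SCCHN with nivolumab (SAP Table 2: r1 = 3, n1 = 16), the probability of stopping at Stage 1 is P(X ≤ 3) with X binomial(16, p). This reproduces SAP Table 11:

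| True response rate | Computed | Stated |
|---|---|---|
| 15% | 78.99% | 79.0% |
| 20% | 59.81% | 59.8% |
| 25% | 40.50% | 40.5% |
| 30% | 24.59% | 24.6% |
| 35% | 13.39% | 13.4% |

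Expected size per cohort is n1 + (1 − stopping probability) × n2. Summed over the SAP's 18 designs it gives 457.2 under the null and 807.7 under the alternative, as in SAP Table B3.

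**4. Range of tumor shares.** These count evaluable subjects under the Simon rules. The Bayesian rule can also suspend cervical, gastric and SCCHN cohorts at other sizes.

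- SAP Groups F, G, H (endometrial 17 or 51, gastric 16 or 46, SCCHN 16 or 46). Endometrial share runs from 17/(17 + 46 + 46) = 17/109 = 15.6% to 51/(51 + 16 + 16) = 51/83 = 61.4%.
- Current Group F (Protocol Tables 19 and 20: cervical 17 or 51, gastric and SCCHN 16 or 46, melanoma 20 or 50, refractory SCCHN 12, 37 or 57). Cervical share runs from 17/216 = 7.9% to 51/115 = 44.3%. Refractory SCCHN share runs from 12/205 = 5.9% to 57/126 = 45.2%.

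**5. Effect on a pooled 1-year rate.** The documents give no tumor-specific OS, so every rate here is an assumption. The pooled rate is the size-weighted mean, assuming complete follow-up to one year. For the SAP's three doublet cohorts:

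| Assumed 1-year OS (endometrial / gastric / SCCHN) | Only gastric expands (n = 79) | Only endometrial expands (n = 83) |
|---|---|---|
| 50 / 25 / 40% | (8.5 + 11.5 + 6.4)/79 = 33.4% | (25.5 + 4.0 + 6.4)/83 = 43.3% |
| 45 / 35 / 40% | (7.65 + 16.1 + 6.4)/79 = 38.2% | (22.95 + 5.6 + 6.4)/83 = 42.1% |
| 40 / 40 / 40% | 40.0% | 40.0% |

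These are the lowest and highest values over all eight stop-or-continue patterns. Survival within each cohort is the same in both columns; only the mix changes. The triplet sizes (21 or 48, 18 or 50, 18 or 50) give 33.9% to 42.5% under the first set of rates.

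**The case against.** The strongest reply is that the treatment-group wording qualifies only the curves. This stands. The median and landmark sentences name no grouping, SAP 5.2 and 5.3.1 set a default of treatment group by tumor cohort, and Table 2.6.2 supplies a tumor-level summary. A reader might infer that every OS output is pooled, or that the OS results describe tumor mix instead of any regimen in any tumor. The documents do not support either.

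A reader might also take the title of Table 2.6.2 to mean that doublets and triplets are combined within a tumor. That is unlikely. Appendix A uses the same suffix for demographics (Table 1.2.2), where SAP 6.1.1 specifies treatment group and tumor type. The PFS tables carry the same suffix and PFS Figure 4.1.1 is equally unlabelled, so the titles alone do not set OS apart. The 7.3.8 sentence does.

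Two further replies have force. Appendix A is a guideline that can change without an SAP amendment, and Phase 1 has its own OS table (2.6.1), so the sentence may have been written partly with Phase 1 in mind. It is not limited to Phase 1, however, and the only planned OS figure is for Phase 2. Also, no OS contrast between groups is planned: the study is nonrandomized, and Protocol 4.2 confines comparisons to pretreatment conditions. That limits the harm to how the curves are read.

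It is tempting to put one figure on a difference between Groups F and H. That would rest wholly on assumed rates, and Group H moves too. With assumed 1-year OS of 40% cervical, 30% gastric and 35% SCCHN, H is (6.8 + 13.8 + 5.6)/79 = 33.2% if only gastric expands and (20.4 + 4.8 + 5.6)/83 = 37.1% if only cervical expands. Redactions in Protocol Table 5 also prevent a full list of cohorts per group. In Group C2 the only visible cohort is relapsed melanoma, so no pooling is evident there.

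**Conclusion.** The point holds for the curves. SAP 7.3.8 gives Phase 2 OS curves a grouping that departs from the PFS and DOR convention and from the SAP's own Phase 2 default, and nothing in Figure 4.1.2 corrects it. A curve drawn that way weights tumors by which cohorts survived the futility rules. That cohort sizes depend on response follows from the documents' own design figures. The size of any resulting shift cannot be derived from them. In the three-cohort illustration it is 0, about 4 or about 10 percentage points (40.0 to 40.0, 38.2 to 42.1, 33.4 to 43.3), according to how far OS is assumed to differ between tumors.

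For medians and 1- and 2-year rates the finding is only that 7.3.8 leaves the grouping unstated. The likely intention is treatment group and tumor type. Severity is minor: OS is secondary and descriptive, with no test attached.

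**What to change.** In SAP 7.3.8, replace the treatment-group grouping of the Phase 2 OS curves with treatment group by tumor-specific cohort, as SAP 5.2 already has it. State the same grouping for the median and the 1- and 2-year rates. Retitle Figure 4.1.2 and Table 2.6.2 to show it. Any pooled group-level curve should be supplementary only, with the number of subjects per tumor cohort shown beside it.

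The cost is a few words, two titles and more panels in one figure. Intervals per cohort will be wider. At an assumed 1-year rate of 40% without censoring, the approximate 95% half-width is 1.96 × √(0.4 × 0.6/16) = 24 points for a cohort of 16, against 1.96 × √(0.4 × 0.6/49) = 14 points for three stopped doublet cohorts pooled (17 + 16 + 16 = 49). The narrower interval belongs to a mixture that the design does not treat as a unit.

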## 8. SAFETY AND TOLERABILITY

Sample data displays are provided in a separate document.

### 8.1. General Considerations

Summary tables may be replaced with listings when appropriate. For instance, an AE frequency table may be replaced with a listing if it only contains a few unique preferred terms reported on relatively few subjects.

Unless otherwise stated, table summaries will be limited to AEs occurring after the first dose of INCAGN01876, nivolumab, or ipilimumab.

### 8.2. Adverse Events

#### 8.2.1. Adverse Event Definitions

A TEAE is any AE either reported for the first time or worsening of a pre-existing event after first dose of study treatment. Analysis of AEs (as discussed below) will be limited to TEAEs, but data listings will include all AEs regardless of their timing in relation to study treatment administration.

Adverse events will be tabulated by MedDRA PT and SOC. Severity of AEs will be graded using the National Cancer Institute CTCAE. The CTCAE version 4.03 is used for this study. The CTCAE reporting guidelines and grading details are available on the Cancer Therapy Evaluation Program website.

The subset of AEs considered by the investigator to be related to INCAGN01876, nivolumab, or ipilimumab will be considered to be treatment-related AEs and will be summarized. If the investigator does not specify the relationship of the AE to study treatment, the AE will be considered to be treatment-related. The incidence of AEs and treatment-related AEs will be tabulated. In addition, SAEs will also be tabulated.

A grading (severity) scale is provided for each AE term. If the toxicity is not included in the CTCAE v4.03 criteria, it will be rated on a scale of 1 to 5 as follows: 1 = mild, 2 = moderate, 3 = severe, 4 = life threatening, and 5 = death related to AE. All toxicities will be graded based on the worst level reached, not the level they may have reached if they had not been treated. When the intensity of an AE changes over time for a reporting period (eg, between visits), each change in intensity will be collected as an AE until the event resolves. Only the worst grade will be reported in AE summaries. Also, the Grade 3 or higher AEs will be reported in a listing.

Any missing onset date, causality, or severity must be queried for resolution. Unresolved missing causality and severity will be handled according to the following rules:

- An unresolved missing causality will be considered treatment-related.
- An unresolved missing severity will be identified as an unknown severity.

For purposes of analysis, all AEs will be considered TEAEs unless the AE can unequivocally be defined as not treatment emergent.

### **8.2.2. Dose-Limiting Toxicities**

The number of subjects with DLTs and the type of DLT will be listed by dose level and treatment group. An AE for a subject will be identified as a DLT if the event is recorded as a protocol-defined DLT on the AE CRF.

### **8.2.3. Maximum Tolerated Dose**

The MTD, or PAD, is defined as a dose that provides a maximal biochemical effect, or an increase in biomarkers of immune activity of INCAGN01876 when given in combination with immune therapies.

- In Phase 1 of the study, the MTD will be defined as 1 dose level below that at which  $\geq$  one-third of subjects in a particular cohort have DLTs.
- In Phase 2 of the study, toxicities will continue to be monitored. If the cumulative incidence of Grade 3 or higher related AEs occurs in  $> 40\%$  of subjects in a particular treatment group after 6 subjects have been enrolled, then further enrollment may be interrupted until the sponsor, investigators, and regulatory authorities (if applicable) determine the appropriate course of action (eg, lower the dose of INCAGN01876, change dose frequency). If a treatment group is discontinued due to toxicity, it may be re-initiated at a previously tested lower dose level and/or alternate dosing schedule.

- All AEs, regardless of the time of occurrence on study, may be considered in DLT determination purposes.

## **8.2.4. Adverse Events of Special Interest or Adverse Events of Clinical Interest**

### **8.2.4.1. Immune-Related Adverse Events**

The number of subjects with irAEs and type of irAE will be listed by treatment group and dose level for the Phase 1 FAS population and by treatment group and tumor type in the Phase 2 FAS population. Adverse event terms will be reviewed periodically without respect to treatment group by the medical monitor and clinical scientist to determine which AE terms correspond to irAEs. This periodic review may also occur after database lock. The medical monitor and clinical scientist will also review investigator-reported AEs to determine whether they qualify as irAEs. For example, a rash will be counted as an irAE even if the investigator did not report it as an irAE.

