1.4. Potential Risks and Benefits of the Combination Regimens

The principle toxicities of administering agents that modulate the immune system are irAEs including skin manifestations, pneumonitis, enterocolitis, and endocrinopathies. Immune-related AEs have been reported in subjects treated with nivolumab and ipilimumab. As the use of immunotherapies become more prevalent, guidelines for the management of irAEs continue to evolve. Careful monitoring, early diagnosis, and treatment with corticosteroids for more severe events is recommended. The time of onset of irAEs varies, with skin manifestations and GI toxicity seen early and elevated liver enzymes and endocrinopathies appearing later

(Weber et al 2015). Subjects enrolled in this study will be carefully monitored for the onset of irAEs, and guidelines for the management of these toxicities are provided in the Protocol and in the prescribing information for nivolumab and ipilimumab.

[REDACTED]

[REDACTED]

[REDACTED]

[REDACTED]

[REDACTED]

[REDACTED]

[REDACTED]

[REDACTED]

[REDACTED]

[REDACTED]

[REDACTED]

[REDACTED]

[REDACTED]

[REDACTED]

[REDACTED]

[REDACTED]

[REDACTED]

[REDACTED]

[REDACTED]

[REDACTED]

[REDACTED]

[REDACTED]

[REDACTED]

[REDACTED]

[REDACTED]

[REDACTED]

[REDACTED]

[REDACTED]

[REDACTED]

[REDACTED]

[REDACTED]

[REDACTED]

[REDACTED]

[REDACTED]

[REDACTED]

[REDACTED]

[REDACTED]

[REDACTED]

[REDACTED]

[REDACTED]

[REDACTED]

[REDACTED]

[REDACTED]

[REDACTED]

[REDACTED]

[REDACTED]

[REDACTED]

[REDACTED]

[REDACTED]

[REDACTED]

[REDACTED]

[REDACTED]

- [REDACTED]
- [REDACTED]
- [REDACTED]
- [REDACTED]

[REDACTED]

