#### **8.2.4.1.1. Adverse Events Identified as Incyte MedDRA Queries**

Prospectively defined Incyte MedDRA Queries will be used to conduct analyses to evaluate the safety profile. Incyte MedDRA Queries are queries constructed by Incyte based on MedDRA preferred terms identified through review of standardized MedDRA queries for clinically relevant terms. Sets of included terms will be identified and archived before database lock for the individual studies. Incyte MedDRA Queries searches are to be conducted for the following TEAEs: hemorrhage events, dizziness, weight gain, thrombotic events, urinary tract infections, herpes zoster infections, tuberculosis, hepatitis B reactivation, and infections other than those stated previously. In addition, these other infections will be analyzed by subcategories of upper respiratory tract infections, lower respiratory tract infections, skin and soft tissue infections, alimentary tract infections, other viral infections, and miscellaneous infections with each tabulated by MedDRA preferred term.

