- Summary of TEAEs leading to INCAGN01876 dose reduction by SOC and PT
- Summary of TEAEs leading to any dose interruption by SOC and PT
- Summary of TEAEs leading to discontinuation of INCAGN01876 by SOC and PT
- Summary of treatment-emergent irAEs (investigator identified) by SOC and PT
- Summary of treatment-emergent irAEs (sponsor identified) by SOC and PT
- Summary of treatment-emergent irAEs (investigator identified) by SOC, PT, and maximum severity
- Summary of Grade 3 or higher treatment-emergent irAEs (investigator identified) by SOC and PT
- Life table estimate of time to first Grade 3 or higher TEAEs
- Summary of TEAEs leading to death by SOC and PT
- Summary of infusion reactions

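### The sponsor's irAE classification may continue after database lock, and no planned table counts sponsor-identified irAEs by severity or at Grade 3 or higher

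*SAP*

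**What the plan says.** Protocol 1.4 describes irAEs as the main toxicities of immune-modulating agents and names "skin manifestations, pneumonitis, enterocolitis, and endocrinopathies".

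SAP 8.2.4.1 sets out the sponsor's classification: "Adverse event terms will be reviewed periodically without respect to treatment group by the medical monitor and clinical scientist". It goes on: "This periodic review may also occur after database lock". It gives no term list, no cut-off date and no rule for marking late changes. Its one example is that "a rash will be counted as an irAE even if the investigator did not report it as an irAE".

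The next subsection, 8.2.4.1.1, covers the sponsor's MedDRA queries and is stricter: "Sets of included terms will be identified and archived before database lock for the individual studies".

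SAP 8.2.5 plans one sponsor-based irAE summary, "Summary of treatment-emergent irAEs (sponsor identified) by SOC and PT". The two severity-based irAE summaries rest on the investigator's label. One is by maximum severity; the other is "Summary of Grade 3 or higher treatment-emergent irAEs (investigator identified) by SOC and PT". Appendix A repeats these choices in Tables 3.2.16 to 3.2.19 and adds Listings 2.6.9 (investigator) and 2.6.10 (sponsor).

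**The concern.** There are two separate weaknesses, and they touch different outputs.

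The first is timing. The trial is open-label. A classification that may be revised after lock, with no freeze date and no label for late changes, leaves the reader unable to tell a prespecified irAE set from one adjusted with final data in view. The SAP already applies the better practice to its other queries.

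The second is consistency. The SAP recognises irAEs that the investigator did not report as such, then leaves them out of both tables that show how severe irAEs were. One of those, 3.2.19, is the only irAE table type marked for the body of the report. The severe-irAE figure that most readers will see therefore uses a narrower definition than the SAP's own counting rule.

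**Working it through.** The documents give no irAE counts and no figure to reproduce, so this is a check of the text. Setting the planned irAE outputs in SAP 8.2.5 and Appendix A side by side:

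| Output | irAE set | Breakdown | In-text | Can after-lock sponsor review change it? |
|---|---|---|---|---|
| Tables 3.2.16.1/2 | Investigator | SOC, PT | No | No |
| Tables 3.2.17.1/2 | Sponsor | SOC, PT | No | Yes |
| Tables 3.2.18.1/2 | Investigator | SOC, PT, maximum severity | No | No |
| Tables 3.2.19.1/2 | Investigator | SOC, PT, Grade 3 or higher | Yes | No |
| Listing 2.6.9 | Investigator | Listing | – | No |
| Listing 2.6.10 | Sponsor | Listing | – | Yes |

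**Step 1, timing.** On the plan's own labels, after-lock review can move Table 3.2.17 and Listing 2.6.10 and nothing else in the table. The contrast with 8.2.4.1.1 is direct: query terms such as dizziness and weight gain are fixed before lock, while the sponsor's irAE list is not.

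**Step 2, severity.** Sponsor-identified irAEs have a SOC/PT table and a listing. They have no maximum-severity table and no Grade 3 or higher table.

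**Step 3, can the missing count be recovered from other tables?** Tables 3.2.5.1/2 cover every Grade 3 or higher treatment-emergent event, and 3.2.4.1/2 give maximum severity for all such events. Both are by SOC and PT without an irAE flag. Adding preferred-term rows does not give subjects, because one subject can appear under several terms. The term alone may not settle irAE status either, since 8.2.4.1 also provides for review of investigator-reported events. The overall AE summary in 8.2.5 has no irAE line. A hand count from Listing 2.6.10 might be possible if the listing shows grade, but the SAP does not give its columns.

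**Step 4, do any decisions use the sponsor list?** DLTs are taken from the AE CRF (SAP 8.2.2). The Phase 2 rule of more than 40% uses Grade 3 or higher INCAGN01876-related AEs (Protocol 4.1.2). Neither uses the sponsor irAE set. The DMC reviews irAE rates (SAP 9.1.1), and the SAP does not say which set that means. That review is interim, so after-lock changes cannot reach it.

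**Step 5, size.** Let N be subjects, I those with an investigator-identified Grade 3 or higher irAE, and S further subjects whose only such event was recognised by the sponsor. Table 3.2.19 shows I/N; a count including both is (I + S)/N. As illustration only, with assumed N = 100, I = 15 and S = 3 to 8, these are 15/100 = 15% against 18/100 = 18% to 23/100 = 23%. None of these inputs comes from the documents.

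**The case against.** The case for leaving the plan alone has real substance.

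- The terms are reviewed without regard to treatment group. This is a genuine safeguard, though partial in an open-label trial.
- Because the trial is open-label, the sponsor sees data throughout, so freezing the list just before lock does not rule out result-driven classification. That is true. A freeze still fixes what was prespecified and makes later changes visible, which the present wording does not.
- The SAP's only example adds an irAE. Removal is not described, but it is not excluded either.
- The Protocol (5.4.7 and the footnote to Table 6) makes an irAE a diagnosis of exclusion, which favours the investigator's case-level judgement for severity. This supports keeping the investigator tables. It does not explain why the SAP defines a wider set and then gives no severity for it.
- Tables 3.2.16 and 3.2.17 already make disagreement between investigator and sponsor visible. They do so by SOC and PT, not by grade.
- Appendix A calls its table list a guideline, so extra tables may need no SAP amendment. That makes the change cheaper; it does not remove the gap.

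A reader might also infer from the query list in 8.2.4.1.1 ("hemorrhage events, dizziness, weight gain, thrombotic events, urinary tract infections, herpes zoster infections, tuberculosis" and others) that the special-interest figure, 4.90.1, omits the immune events. The documents do not support this. Section 8.2.4, on events of special interest, itself opens with irAEs, and nothing says the figure is built only from the queries. Nor are those queries unrelated to risks in the Protocol: upper respiratory tract infection is named for nivolumab in 1.3.1.2, and thrombocytopenia with significant bleeding is a DLT in Table 6.

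**Conclusion.** Both points stand as reporting weaknesses. The sponsor-identified irAE set has no freeze and can change after lock. No planned table reports that set by severity or gives the number of subjects with a sponsor-identified Grade 3 or higher irAE.

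Three stronger readings are tempting and should be set aside. A reader might infer that the Grade 3 or higher irAE numerator can itself move after lock; it cannot on the plan's labels, because Table 3.2.19 uses investigator-identified events. A reader might infer that severe toxicity is hidden; it is not, because Tables 3.2.5.1/2 are in-text and cover all Grade 3 or higher treatment-emergent events, SAP 8.2.1 also calls for a listing of Grade 3 or higher AEs, and sponsor-identified irAEs appear in Table 3.2.17 and Listing 2.6.10. A reader might infer that dose or stopping decisions are affected; the DLT and Phase 2 toxicity rules do not use the sponsor list.

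The size of any understatement in Table 3.2.19, relative to the SAP's wider definition, is unknown. It depends wholly on how many Grade 3 or higher irAEs only the sponsor identifies. The illustration further assumes that sponsor review only adds events.

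**What to change.** 1. In SAP 8.2.4.1, delete the after-lock sentence. State that the sponsor's irAE term list will be archived before database lock, as 8.2.4.1.1 already requires for the other queries, and that any later change will be reported separately as post hoc.
2. In SAP 8.2.5 and Appendix A, add sponsor-identified versions of Tables 3.2.18.1, 3.2.18.2, 3.2.19.1 and 3.2.19.2. Mark the Grade 3 or higher pair in-text beside the investigator versions, which stay.

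The cost is SAP wording, one term list fixed earlier and four repeat tables. The reported Grade 3 or higher irAE rate may look less favourable on the wider definition. Sample size, power and type I error are unchanged.
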